### **16.1.2. SERIOUS ADVERSE EVENTS AND DEATH**

Serious adverse events (SAEs) are those events recorded as “Serious” on the Adverse Events page of the eCRF. A summary of SAEs by SOC and PT will be prepared.

AEs leading to death are those events which are recorded as “Fatal” on the Adverse Events page of the eCRF. Deaths may also be recorded on the End of Treatment page and the Completion/Withdrawal from Study page of eCRF. A listing all deaths will be prepared based on these sources.

### **16.1.3. EXTRAPYRAMIDAL TEAEs**

Treatment-emergent extrapyramidal adverse events will be defined by the Standard MedDRA Query (SMQ) labeled as Extrapyramidal Syndrome. The number and percentage of subjects with at least one AE PT mapped to an extrapyramidal term contained in the SMQ will be presented. The extrapyramidal terms will be summarized as well. Separate tables will be presented for the narrow and broad interpretation of the SMQ.

#### 16.1.4. ABUSE-RELATED TEAEs

TEAEs will be categorized as defined in the table below to monitor signals of potential abuse of ITI-007. The number and percentage of subjects with at least one abuse-related TEAE will be summarized along with a summary of the PTs below.

**Table D: Abuse-Related PTs**

Category	Applicable PTs
Euphoria	Euphoric mood; Elevated mood; Feeling abnormal; Feeling drunk; Feeling of relaxation; Dizziness; Thinking abnormal; Hallucination; Inappropriate affect
Impaired attention, cognition, and mood	Somnolence; Sedation; Mood disorders and disturbances
Dissociative/psychotic	Psychosis; Aggression; Confusion and disorientation
Other related terms	Drug tolerance; Habituation; Drug withdrawal syndrome; Substance-related disorders

#### 16.2. LABORATORY EVALUATIONS

Results from the central laboratory will be included in the reporting of this study for hematology, clinical chemistry, and urinalysis. A list of laboratory assessments to be included in the outputs is included in the protocol, [Section 6.5](#). Summary statistics will be presented in SI and US conventional units. Shift tables and abnormalities based on normal range criteria will be presented using SI units only.

Local laboratory tests will be utilized if necessary for this study. Local laboratory results will be converted to the same units as central laboratory tests and summarized together with the central results. In cases where both central and local laboratory results are available for the same time point, the central result will be used for the by-visit summaries. When central results are unavailable, local results will be summarized.

Quantitative laboratory measurements reported as “< X”, i.e. below the limit of quantitation (BLQ), or “> X”, i.e. above the upper limit of quantitation (ULQ), will be converted to X for the purpose of quantitative summaries, but will be presented as recorded, i.e. as “< X” or “> X” in the listings.

All laboratory samples are to be collected after an overnight fast. Results for glucose, insulin, and triglycerides collected non-fasting will be excluded from descriptive statistics but will appear in the data listings.

The following summaries will be provided for laboratory data:

- Actual values and change from baseline by visit (for quantitative measurements)
- Incidence of abnormal values according to normal range criteria
- Shifts from baseline according to normal range criteria (for quantitative and categorical measurements)
- Shifts from baseline according to the markedly abnormal criteria defined in [Section 16.2.1](#) (for quantitative and categorical measurements)
- Listing of laboratory values meeting markedly abnormal criteria
- Incidence of liver function-related values meeting pre-defined criteria as defined in [Section 16.2.2](#) during the On-Treatment Period and the entire Part A study

### **16.2.1. LABORATORY REFERENCE RANGES AND MARKEDLY ABNORMAL CRITERIA**

Quantitative laboratory measurements will be compared with the relevant laboratory reference ranges in SI units and US Conventional units and categorized as:

- Low: Below the lower limit of the laboratory reference range.
- Normal: Within the laboratory reference range (upper and lower limit included).
- High: Above the upper limit of the laboratory reference range.

In addition to the high and low quantitative laboratory assignments (as identified by means of the laboratory reference ranges), markedly abnormal quantitative safety (and other) laboratory assessments will also be identified in accordance with the predefined markedly abnormal criteria as presented in the table below.

**Table E: Markedly Abnormal Values for Laboratory Evaluations**

Haematology Parameter	Markedly Abnormal Range
Hemoglobin	Male: $\leq 11.5$ g/dL
	Female: $\leq 9.5$ g/dL
Hematocrit	Male: $\leq 37\%$

	Female: $\leq 32\%$
WBC	$\leq 2.8 \times 10^3 \text{ cells}/\mu\text{L}$
	$\geq 16 \times 10^3 \text{ cells}/\mu\text{L}$
Neutrophils (percent)	$\leq 15\%$
Eosinophils (percent)	$\geq 10\%$
Platelet Count	$\leq 75 \times 10^3 \text{ cells}/\mu\text{L}$
	$\geq 700 \times 10^3 \text{ cells}/\mu\text{L}$
Chemistry Parameter	Markedly Abnormal Range
Alkaline Phosphatase	$\geq 2 \times \text{ULN}$
GGT	$\geq 3 \times \text{ULN}$
Albumin	$< 2.5 \text{ g/dL}$
Glucose	$< 45 \text{ mg/dL}$
	$> 160 \text{ mg/dL}$
Sodium	$< 130 \text{ mmol/L}$
	$> 150 \text{ mmol/L}$
Potassium	$< 3 \text{ mmol/L}$
	$> 5.5 \text{ mmol/L}$
Chloride	$< 90 \text{ mmol/L}$
	$> 115 \text{ mmol/L}$
Calcium	$< 7 \text{ mg/dL}$
	$> 12 \text{ mg/dL}$
Blood Urea Nitrogen	$\geq 30 \text{ mg/dL}$
Creatinine	$\geq 2.0 \text{ mg/dL}$

HbA 1c	≥ 7.5%
Prolactin	≥ 5 x ULN
Total Cholesterol	≥ 300 mg/dL
LDL Cholesterol	≥ 200 mg/dL
Triglycerides	≥ 300 mg/dL
Urinalysis Parameter	Markedly Abnormal Range
RBC	> 10 cells/hpf
WBC	> 20 cells/hpf

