6.5 Laboratory Analyses

Blood and urine samples collected from patients will be forwarded to a central laboratory for analysis. Further details regarding sample collections, processing and specific testing can be found in the study reference manual.

All samples for clinical laboratory analysis will be collected after an overnight fast (≥ 10 hours), for all visits subsequent to screening, prior to dosing with study drug. Samples for clinical laboratory analysis will be used only for the evaluation of safety and tolerability.

Any abnormal laboratory test results (hematology, clinical chemistry, or urinalysis) or other safety assessments (e.g., ECGs, vital sign measurements), including those that worsen from baseline, felt to be clinically significant, in the medical and scientific judgment of the investigator, are to be recorded as AEs or SAEs.

However, any clinically significant safety assessments that are associated with the underlying disease, unless judged by the investigator to be more severe than expected for the patient's condition, are not to be reported as AEs or SAEs.

The following clinical analytes will be determined:

Hematology: hematocrit; hemoglobin; HbA_{1c}; red blood cell count with indices (mean corpuscular volume, mean corpuscular hemoglobin, and mean corpuscular hemoglobin concentration); reticulocytes; white blood cell count and differential (neutrophils, lymphocytes, monocytes, eosinophils, and basophils) reported as percent (%) and absolute values; and platelets (platelet count, prothrombin time and partial thromboplastin time, international normalization ratio).

Clinical chemistry: albumin; alkaline phosphatase; blood urea nitrogen; gamma-glutamyl transferase; calcium; creatinine; glucose; insulin; cholesterol (high-density lipoprotein and low-density lipoprotein [LDL] [calculated] and homogenous LDL will be reported, and homogenous LDL will be reflexed if a patient's triglycerides are >400); triglycerides; phosphate; potassium; prolactin, ALT; AST; lactate dehydrogenase; sodium; chloride; bilirubin (total, direct); total protein; uric acid; creatine phosphokinase; and thyroid panel (at screening only, thyroid-stimulating hormone will be assayed and if the result is abnormal, the free thyroxine and free triiodothyronine will be assayed).

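### SAP Table E judges neutrophils and eosinophils by percentage only, so a lower absolute neutrophil count can go unflagged as markedly abnormal while a higher one is flagged

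*SAP*

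**What the plan says.** SAP section 16.2.1 sorts laboratory results in two tiers.

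- **First tier.** "Quantitative laboratory measurements will be compared with the relevant laboratory reference ranges in SI units and US Conventional units and categorized as" Low, Normal or High.
- **Second tier.** On top of that, values are called markedly abnormal if they meet the limits in Table E.

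The white-cell rows of Table E are:

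- total WBC: at or below 2.8, or at or above 16, ×10³ cells/µL;
- the row beginning "Neutrophils (percent": at or below 15%;
- the row beginning "Eosinophils (percent": at or above 10%.

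Total WBC is the only one of the three stated as a count. SAP section 16.2 uses the second tier for a shift table and for a "Listing of laboratory values meeting markedly abnormal criteria". For the parameters to be reported it refers to protocol section 6.5, which asks for "white blood cell count and differential (neutrophils, lymphocytes, monocytes, eosinophils, and basophils) reported as percent (%) and absolute values". The absolute counts are therefore already in the data.

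**The concern.** A differential percentage depends on every other white-cell line as well as the one of interest. The same 15% is a small count when total WBC is low and a much larger one when it is high. A limit placed on the percentage therefore does not pick out the patients with the lowest neutrophil counts or the highest eosinophil counts.

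The markedly abnormal tier exists to separate large departures from marginal ones. If it selects the wrong patients for two cell lines, the shift table and listing built on it can omit a patient with the more extreme count and include one with the milder count. What is at stake is case-finding in the Part A safety report.

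**Working it through.** The plan states no figure to reproduce, because Table E only sets limits. The check is direct arithmetic, in units of ×10³ cells/µL throughout.

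**Inputs.** From Table E: WBC ≤ 2.8 or ≥ 16, neutrophils ≤ 15%, eosinophils ≥ 10%. The WBC and percentage values in step 1 are illustrations. Neither document gives absolute limits for these cells or a white-cell distribution, so those are assumptions and are shown as ranges.

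**Step 1: worked cases.** Absolute count = WBC × percentage / 100.

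| Cell | WBC | Percent | Absolute count | Flagged in Table E? |
|---|---|---|---|---|
| Neutrophils | 2.9 | 16 | 0.46 | no |
| Neutrophils | 5.0 | 16 | 0.80 | no |
| Neutrophils | 3.5 | 25 | 0.88 | no |
| Neutrophils | 12 | 15 | 1.80 | yes |
| Eosinophils | 4.0 | 10 | 0.40 | yes |
| Eosinophils | 14 | 9 | 1.26 | no |

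A neutrophil count of 1.80 is markedly abnormal and 0.46 is not. An eosinophil count of 0.40 is markedly abnormal and 1.26 is not. Neither inversion depends on any reference limit.

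**Step 2: lowest neutrophil count that can escape.** A value escapes the low-WBC and neutrophil rules only if WBC > 2.8 and the percentage > 15. Its count must then exceed 2.8 × 0.15 = 0.42. Conversely, for any count A above 0.42 there are WBC values between 2.8 and A / 0.15 at which neither rule fires. Counts of 0.42 or less are always flagged.

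**Step 3: where the gaps lie for assumed absolute limits.**

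- A neutrophil count below a limit T can go unflagged when WBC is above 2.8 and below T / 0.15. That upper bound is 3.33 for T = 0.5, 6.67 for 1.0, 10.0 for 1.5 and 13.3 for 2.0.
- Eosinophils at exactly 10% are flagged while not exceeding an upper limit U when WBC is at most U / 0.10. That is 3.5, 4.0, 5.0 and 6.0 for U = 0.35, 0.40, 0.50 and 0.60.

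The mismatch appears at every value tried.

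**Step 4: how often it might happen.** Let L be the non-neutrophil white count and A the neutrophil count. The flag fires if A + L ≤ 2.8 or A / (A + L) ≤ 0.15, that is, if A ≤ max(2.8 − L, (0.15 / 0.85) × L). The boundary is 0.42 at L = 2.4, 0.49 at L = 2.8 and 0.56 at L = 3.2.

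Simulation with L lognormal, and A spread evenly over each band and independent of L, gives the share unflagged:

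| Assumed L: mean (SD) | A below 0.5 | A 0.5–1.0 | A below 1.0 |
|---|---|---|---|
| 2.0 (0.5) | 2% | 41% | 21% |
| 2.4 (0.6) | 3% | 66% | 34% |
| 2.8 (0.7) | 3% | 77% | 40% |
| 3.2 (0.8) | 2% | 77% | 39% |

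This treats a fall in neutrophils as selective, with the other cell lines unaffected. The even spread of A is for illustration only.

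**The case against.** The strongest reply is that Table E is not the only place where these values appear. SAP section 16.2 also plans actual values and changes from baseline by visit, incidence outside the normal range, and shifts by normal range. A neutrophil count of 0.46, 0.80 or 0.88 would be counted Low there whenever it lies below the laboratory's lower limit. SAP section 8 adds patient data listings. Under protocol section 6.5, results that the investigator judges clinically significant are in general recorded as adverse events, and so reach the by-arm tables. Table E also contradicts nothing in the protocol, which asks for both forms of the differential without saying which should drive an outlier flag. The WBC row is an absolute backstop, and at the lowest counts the present rules work well. Few such events are to be expected in 6 weeks.

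Most of this stands, and it limits the point. A reader might infer that a patient with low neutrophils is not flagged anywhere, or that a difference between arms would go unseen. The documents do not support either: the Low shifts and change-from-baseline summaries remain. A reader might also infer that most counts of 0.5–1.0 are missed, but that depends on an assumed distribution and fails at a mean L of 2.0 (41%). Words such as clearly low or normal would need absolute limits that the documents do not give.

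What the reply does not remove is the inversion within the second tier. Low does not separate a marginal value from 0.46. The tier meant to do so uses the wrong scale for these two cell lines. The WBC backstop stops at 2.8.

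**Conclusion.** The point holds as a minor one. For neutrophils and eosinophils, Table E can leave the more extreme absolute count unflagged as markedly abnormal and flag the milder one. That conclusion, and the 0.42 bound above which a neutrophil count can escape, follow from the Table E limits alone.

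The frequency is less certain. The range of about 41–77% unflagged for counts of 0.5–1.0, and about 2–3% below 0.5, holds only under the assumed distributions. No frequency was estimated for eosinophils.

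The loss is confined to the markedly abnormal shift table and listing in Part A safety reporting. The primary and key secondary analyses, power and type I error are not touched.

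**What to change.** Before unblinding, add an absolute neutrophil row and an absolute eosinophil row to Table E beside the percentage rows. The sponsor's medical and laboratory reviewers should set the cut-offs, since the documents offer no basis for choosing them. Run the markedly abnormal shift table and listing on the new rows as well.

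The cost is two table rows and minor programming, with no new data to collect. The downside is that a few more patients with benign values will be flagged, in all arms.

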### 16.2.2. LIVER FUNCTION RELATED CRITERIA

Liver function-related laboratory tests will be summarized in accordance to the criteria listed below in [Table F](#).

**Table F: Liver Function Pre-defined Criteria**

Liver Function Parameter	Criteria
ALT	≥ 3 x ULN
	≥ 5 x ULN
AST	≥ 3 x ULN
	≥ 5 x ULN
GGT	≥ 3 x ULN
	≥ 5 x ULN
Total Bilirubin (in combination with ALT or AST criteria)	> 1.5 x ULN
	> 2 x ULN
CPK	≥ 5 ULN
Hy's Law	Criteria

ALT or AST	$\geq 3 \times \text{ULN}$
Total Bilirubin	$> 2 \times \text{ULN}$
Alkaline phosphatase	$< 2 \times \text{ULN}$

### 16.3. ECG EVALUATIONS

Results from the central Electrocardiogram (ECG) Reading will be included in the reporting of this study.

The following ECG parameters will be reported for this study:

- PR Interval (msec);
- QRS Interval (msec);
- QT Interval (msec);
- RR Interval (msec);
- QTcF Interval (msec) [derived by central ECG];
- QTcB Interval (msec) [derived by central ECG];
- HR (bpm);
- Overall assessment of ECG;

ECGs which are collected in triplicate will be analyzed as an average of the non-missing measurements at each time point. For the overall assessment, there are five possible results for each triplicate from the central cardiologist: 'Abnormal, Significant', 'Abnormal Insignificant', 'Incomplete Analysis', 'Normal', and 'Uninterpretable'. Overall assessments with a result of 'Incomplete Analysis' or 'Uninterpretable' will be considered missing. Triplicates will be summarized according to the worst non-missing assessment and categorized in the following order, 'Abnormal Significant', 'Abnormal, Insignificant' and 'Normal'. For single ECGs, the measurements and assessments will be analyzed as collected according to the categories described previously.

The single or average of the three ECG recordings corresponding to the triplicate collected pre-dose at Visit 2 on Day 1 will be considered baseline.

The following summaries will be provided for ECG data:

- Actual and change from baseline by visit (for quantitative measurements)
- Incidence of abnormal and normal ECGs by visit
- Shifts from baseline to each visit and time point according to markedly abnormal criteria (for quantitative measurements and categorical measurements)
- Incidence of markedly abnormal results by categories defined in [Section 16.3.1](#)
- Listing of ECG values meeting markedly abnormal criteria

### **16.3.1. ECG MARKEDLY ABNORMAL CRITERIA**

Markedly abnormal quantitative ECG measurements will be identified in accordance with the following predefined markedly abnormal criteria:

Absolute values for QT, QTcB, and QTcF intervals will be classified as:

- >450 msec
- >480 msec
- >500 msec

Change from Baseline for QT interval, QTcB interval, and QTcF will be classified as:

- >30 msec increase from baseline
- >60 msec increase from baseline

### **16.4. VITAL SIGNS**

The following vital sign measurements will be reported for this study:

- Systolic blood pressure (mmHg) after 10 minutes in supine position, 1 minute sitting, immediately upon standing and 3 minutes after standing
- Diastolic blood pressure (mmHg) after 10 minutes in supine position, 1 minute sitting, immediately upon standing and 3 minutes after standing
- Pulse rate (bpm) after 10 minutes in supine position, 1 minute sitting, immediately upon standing and 3 minutes after standing
- Respiratory rate (breaths/min)

- Oral temperature (°C)
- Weight (kg)
- BMI (kg/m^2) [derived – see [Section 11](#)]
- Waist circumference (cm)

Vital signs, including systolic blood pressure, diastolic blood pressure, pulse rate, and respiratory rate, are collected on pre-specified study days. The assessment at Visit 2 on Day 1 will be considered baseline.

BMI measurements classify a subject's weight status as underweight, normal, overweight, or obese using [Table G](#). Shifts from Baseline to Day 43 will be produced by treatment group for the SAF Set to show the percentage of subjects who fall into each BMI category combination.

**Table G: BMI Weight Status Categories**

BMI (kg/m  )	Weight Status
< 18.5	Underweight
18.5 ≤ BMI < 25.0	Normal
25.0 ≤ BMI < 30	Overweight
30.0 ≤ BMI	Obese

The following summaries will be provided for vital signs data:

- Actual and change from baseline by visit
- BMI shift summaries
- Incidence of markedly abnormal values
- Shifts from baseline by visit and time point according to markedly abnormal criteria
- Listing of subjects meeting markedly abnormal criteria

#### **16.4.1. VITAL SIGNS MARKEDLY ABNORMAL CRITERIA**

Markedly abnormal quantitative vital sign measurements will be identified in accordance with the following predefined markedly abnormal criteria in the table below.

**Table H: Markedly Abnormal Criteria for Vital Signs**

Variable (Unit)	Low	High
SBP (mmHg)	≤ 90 mmHg AND decrease from baseline ≥ 20 mmHg	≥ 180 mmHg AND increase from baseline ≥ 20 mmHg
DBP (mmHg)	≤ 50 mmHg AND decrease from baseline ≥ 15 mmHg	≥ 105 mmHg AND increase from baseline ≥ 15 mmHg
Pulse Rate (bpm)	≤ 50 bpm AND decrease from baseline ≥ 15 bpm	≥ 120 bpm AND increase from baseline ≥ 15 bpm
Weight (kg)	percentage change from baseline ≤ -7.0	percentage change from baseline ≥ 7.0

## 16.5. PHYSICAL EXAMINATION

The following summaries will be provided for physical examination data:

- Incidence of abnormalities at screening
- Incidence of abnormalities post baseline at Weeks 3, 6, and 8 (Days 22, 43, and 57)  
(Follow up/early discontinuation)

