6.1.3 Modified Physical Examination

A modified physical examination, including neurological and excluding genital/rectal examinations, will be performed. The examination should include evaluation of height (at screening only [m]); body weight (kg); waist circumference (cm); appearance and skin; head and neck; eyes, ears, nose, and throat; chest and lungs; heart; abdomen; and extremities. All physical examination findings must be documented in the patient's study chart and also recorded in the eCRF.

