6.3.2.8 Physical and Neurological Examination

The physical and neurological examinations will be conducted at screening and periodically throughout the study, as scheduled (Table 6–1 and Table 6-2 for Parts A and B, respectively). Details of the physical and neurological examinations are presented in Section 6.1.3.

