7.1.5 Safety Endpoints (Parts A and B)

- AEs;
- YMRS total score;
- MADRS score (safety endpoint for Part B only);
- C-SSRS scores;
- AIMS scores;
- BARS scores;
- SAS score;
- Physical examination and neurological findings;
- Vital signs (blood pressure, heart rate), weight, and height (height, only at screening);
- ECGs;
- Clinical laboratory evaluations.

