7.5.8 Safety Analyses (Parts A and B)

All safety parameters will be summarized using the Safety Analysis Set.

Medical history, prior medications, concomitant medications, and compliance/exposure will be summarized by treatment group using descriptive statistics. Safety data such as reported and observed AEs, TEAEs, SAEs, clinical laboratory results, vital signs, physical examinations and neurological findings, ECGs, and the different rating scales (YMRS, C-SSRS, AIMS, BARS, and SAS) will be summarized by visit (Part A and Part B) and treatment group (Part A). Parameters planned to be collected more than once at pre-specified timepoints will be analyzed as an average of the measures for the relevant time point, including screening and baseline.

[figure not shown]
Observed and reported AE terms will be coded using the latest version of MedDRA. TEAEs will be defined as any AEs, regardless of the relationship to study drug, that occur or worsen in intensity after the first dose of study drug and within 14 days after the last dose of study drug. Study-drug-related TEAEs will be defined as any AEs that are considered by the investigator to be either possibly, probably, or definitely related to study drug. If relationship to study drug is missing, the TEAE will be considered as treatment-related. TEAEs, and SAEs will be listed summarized by SOC, PT, relationship to study drug, intensity (Part A and Part B) and treatment group (Part A). Patients who discontinue study or study drug due to an AE will be listed and summarized by SOC and PT (Parts A and B) and by treatment group (Part A).

Laboratory assessments, including hematology and chemistry, vital signs, and ECGs, will be listed and summarized by visit and time point (Parts A and B and by treatment group (Part A). Summaries will include actual and change from baseline values, incidence of abnormal values according to normal range criteria, shifts from baseline to each visit and

time point according to markedly abnormal criteria, and listings of patients meeting markedly abnormal criteria.

The observed and change from baseline in YMRS, AIMS, BARS, SAS and C-SSRS scores will be summarized by visits (Part A and B) and by treatment group (Part A).

Additional details for analyses on safety parameters will be provided in the statistical analysis plan.

A series of approximately 10 horizontal black bars of varying lengths, indicating redacted text.

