**3.2.3. SECONDARY OBJECTIVES - SAFETY**

The safety objectives of Part A of this study are to determine the safety and tolerability of 2 doses of ITI-007 via change in the following safety endpoints:

- Incidence of adverse events (AEs);
- Young Mania Rating Scale (YMRS);
- Columbia Suicide Severity Rating Scale (C-SSRS);
- Abnormal Involuntary Movement Scale (AIMS);
- Barnes Akathisia Rating Scale (BARS);
- Simpson Angus Scale (SAS);
- Clinical laboratory evaluations;
- Electrocardiograms (ECGs);
- Vital sign measurements;
- Physical and neurological examination findings.

[REDACTED]

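### SAP 16.5 counts examination abnormalities at screening and after baseline separately, with no summary that separates new findings from old ones

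*SAP*

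**What the plan says.** SAP 16.5 (Physical Examination) lists two summaries. The first is "Incidence of abnormalities at screening". The second is "Incidence of abnormalities post baseline at Weeks 3, 6, and 8 (Days 22, 43, and 57"), with follow-up and early-discontinuation visits included. The section says nothing about shifts, about restricting to patients who were normal at screening, or about what counts as new or worsened.

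The safety objective in SAP 3.2.3 is to "determine the safety and tolerability of 2 doses of ITI-007 via change in the following safety endpoints", and the list includes "Physical and neurological examination findings". Protocol 7.1.5 names the same item as a safety endpoint for both parts: "Physical examination and neurological findings".

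SAP 16.5 does not mention the neurological examination by name. It comes in through Protocol 6.1.3: "A modified physical examination, including neurological and excluding genital/rectal examinations, will be performed". A pre-treatment examination exists for every patient, because Protocol 6.3.2.8 states that "The physical and neurological examinations will be conducted at screening and periodically throughout the study, as scheduled".

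On analysis, Protocol 7.5.8 says only that these findings, along with other safety data, "will be summarized by visit (Part A and Part B) and treatment group (Part A").

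**The concern.** SAP 16.5 uses *incidence* for the screening count as well as for the post-baseline count. At screening the word can only mean that the finding is present at that visit. Read the same way after baseline, it gives a prevalence: a chronic abnormality noted at screening is counted again at Weeks 3, 6 and 8. Two percentages side by side do not show how many patients went from normal to abnormal, and that transition is what an objective framed as change asks for.

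At stake is how readily the table shows a difference in newly arising findings. Carried-over findings raise the rate in every arm by about the same amount. They pull the risk ratio towards 1 and add variance, and resolution of old findings can offset the appearance of new ones.

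**Working it through.** **1. Baseline reference in each safety section of the SAP**

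| Section | Data | Baseline-referenced summary |
|---|---|---|
| 16.2 | Laboratory | Shifts by normal range and by markedly abnormal criteria |
| 16.3 | ECG | Change, and shifts by markedly abnormal criteria |
| 16.4 | Vital signs, weight, BMI | Change, and shifts |
| 16.6.1 to 16.6.4 | BARS, AIMS, SAS, YMRS | Change from baseline |
| 16.6.5 | C-SSRS | Emergence and worsening relative to baseline |
| 16.5 | Physical examination | None stated |

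In the visible text, the physical examination is the only one of these assessments without such a summary.

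**2. Size of the dilution (illustration)**

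The plan states no figure on this point, so there is nothing to reproduce. Inputs:

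- n = 183 per arm (Protocol 4.1).
- Two-sided alpha 0.05 (the default in SAP 7). SAP 16.5 plans no test, so power serves here only as a scale for sensitivity.
- Assumed: new findings in 2% of placebo patients and 8% of active patients among those normal at screening; pre-existing prevalence p0 from 1% to 40%; all old findings persist.

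Formulas:

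- Rate as planned = p0 + (1 − p0) × new rate, with n = 183 per arm.
- Rate counting new findings only = new rate, with n = 183 × (1 − p0) per arm.
- Power = Φ[(d − 1.96 × SE0)/SE1], where d is the difference in rates, SE0 the pooled and SE1 the unpooled standard error.

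Example at p0 = 20%: placebo 0.20 + 0.80 × 0.02 = 21.6%; active 0.20 + 0.80 × 0.08 = 26.4%; risk ratio 26.4/21.6 = 1.22.

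| p0 | As planned, placebo v active | Risk ratio | Power | New only: risk ratio | New only: power |
|---|---|---|---|---|---|
| 1% | 3.0% v 8.9% | 2.99 | 67% | 4.0 | 75% |
| 2% | 4.0% v 9.8% | 2.48 | 60% | 4.0 | 74% |
| 5% | 6.9% v 12.6% | 1.83 | 45% | 4.0 | 73% |
| 10% | 11.8% v 17.2% | 1.46 | 31% | 4.0 | 71% |
| 20% | 21.6% v 26.4% | 1.22 | 19% | 4.0 | 66% |
| 30% | 31.4% v 35.6% | 1.13 | 13% | 4.0 | 60% |
| 40% | 41.2% v 44.8% | 1.09 | 10% | 4.0 | 53% |

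A second set of assumed rates, new findings 4% versus 1% with 180 per arm, gives the same pattern. Expected z = difference / unpooled standard error:

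| p0 | z, all abnormalities | z, new only |
|---|---|---|
| 1% | 1.54 | 1.82 |
| 2% | 1.36 | 1.81 |
| 10% | 0.78 | 1.74 |
| 20% | 0.55 | 1.64 |
| 30% | 0.43 | 1.53 |

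The gap is wide at prevalences that might apply to any abnormality anywhere in the examination. It is much narrower at the 1% to 2% that may be nearer the mark for one body system.

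**3. Resolution can offset emergence**

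Suppose 20% are abnormal at screening, a quarter of these resolve, and 6.25% of the remaining patients become abnormal. The post-baseline rate is 0.20 × 0.75 + 0.80 × 0.0625 = 0.15 + 0.05 = 20%. The two planned counts would agree, although 5% of all patients had a new finding.

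**The case against.** The strongest answer is that new findings already have a route into the analysis. Protocol 6.3.1 requires all adverse events to be reported whatever their clinical significance, and 6.3.1.7 names physical examinations as one way they are discovered. SAP 16.1 counts as TEAEs only events that start or worsen on or after first dose, so a stable chronic finding is not counted. SAP 16.1.1 tabulates TEAEs with relative risks, confidence intervals and p-values. Signs most relevant to this drug class also have their own analyses: AIMS, BARS and SAS change, extrapyramidal TEAEs by SMQ (16.1.3), weight and BMI. Patient listings are planned (SAP 8).

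Most of this stands, and it limits the consequence. It does not close the gap. Protocol 6.5 asks for abnormal safety assessments to be recorded as adverse events when the investigator judges them clinically significant, so the route depends partly on judgement. The same route exists for laboratory, ECG and vital-sign abnormalities, and the SAP still plans shift tables for those. A listing is not a summary by arm.

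Three further objections are fair. The SAP does not say outright that pre-existing findings are counted after baseline; this is inferred from the use of *incidence* and the absence of any exclusion. The table shells that SAP 8 says accompany the plan were not among the documents, so a shift layout there cannot be ruled out. And restricting an overall count to patients with an entirely normal screening examination would lose anyone with an unrelated old finding. The fix below avoids that.

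**Conclusion.** The point holds as a minor one. SAP 16.5 as worded yields visit prevalences, does not measure the change named in SAP 3.2.3, and is out of step with the other safety sections. The consequence is reduced sensitivity in one descriptive table. Under the assumed 8% versus 2%, a risk ratio of 4.0 would show as anything from 2.99 (p0 = 1%) to 1.09 (p0 = 40%). Those rates and full persistence of old findings are assumptions; the documents give no value for any of them.

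A reader might infer more, and the documents do not support it:

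- *That the table hides a drug effect or biases the comparison.* Carried-over findings are balanced in expectation between randomised arms, the screening count shows any chance imbalance, and findings recorded as adverse events are analysed elsewhere.
- *That a planned test loses power.* SAP 16.5 plans no test. In the 4% versus 1% example, even the new-only z stays below 1.96.
- *That the SAP contradicts the protocol.* Protocol 7.5.8 asks only for summaries by visit and treatment group, and 16.5 is compatible with that.

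**What to change.** In SAP 16.5 add, by treatment group:

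1. A normal/abnormal shift table from screening to each post-baseline visit and from screening to the worst post-baseline result. Present it per body system, with neurological as its own row, among patients examined at screening and at least once after baseline.
2. An overall count of patients with at least one body system shifting from normal at screening to abnormal after baseline. Do not exclude patients who have an old abnormality in a different system.

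State that worsening of an existing abnormality is captured in the TEAE tables. If the shells already contain such a layout, a sentence in 16.5 saying so is enough. The cost is one extra table from data already collected, with no change to visits or assessments.
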